5. METHODOLOGY

5.1. Design of study

Study randomized prospective of intervention with optimization dietetics in people with HIV in treatment antiretroviral with dyslipidemia (Cholesterol total >200mg/dl either LDL cholesterol >160mg/dl) and without treatment lipid-lowering.

5.2. Study population, inclusion/exclusion criteria and subject withdrawal criteria.

Criteria of inclusion:

- Participant \geq 18 years.
- Infection by HIV confirmed by serology.
- Treatment antiretroviral asset (TAR).

- Burden viral undetectable during to the less 12 months (HE allows a blip below 200 copies).
- LDL >140 mg/ dL .
- Mediterranean Diet Adherence Screener (MEDAS) lower to 9 points (low adhesion) to facilitate the detection of changes after the intervention.

Criteria of exclusion:

- Participants in treatment lipid-lowering.
- Treatment with anti-inflammatory chronic.
- Hepatitis B, C or Others conditions inflammatory chronicles active.
- Hypercholesterolemia familiar No treated.
- Hypothyroidism No controlled.
- Impossibility of give he consent.

Criteria of withdrawal:

Subjects may withdraw from the study at any time without obligation to provide a reason. He IP can give of low to a subject of the study by reasons of safety or efficacy.

The reasons of abandonment of the study will be the following:

- Failed of screening: All patient that, a time informed is spoiled in participating in the study, does not meet the inclusion and/or exclusion criteria.
- Withdrawal of the consent: All patient that, by any reason, remove your consent
- Consumption of anti-inflammatory either lipid-lowering drugs during further of 7 days.
- Diagnosis of hypothyroidism either diabetes mellitus.
- Any event adverse that prevent continue any diet indicated.
- Loss of follow-up.

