PROTOCOL OF CLINICAL RESEARCH

Randomized Study to Assess the Impact of Mediterranean Diet Optimization on Metabolic Profile, Immune Activation, and Cardiovascular Risk in People with HIV on ART

Version of the protocol and date	Version: 1.2 date: 06/15/2024
Code of the protocol	
Qualification abbreviated either acronym	VIHMET
Promoter	
CRO (when proceed)	If applicable
Research Team	
Principal Investigator [name] HIV Division. Internal Medicine. Hospital del Mar [contact] e-mail: [contact]
 
Researcher(s) contributor(s) [name] Endocrinology Hospital del Mar, Barcelona [contact] e-mail: [contact]
 
[name] HIV Division. Internal Medicine. [contact] E-mail: [contact]
 
[name] Endocrinology Hospital del Mar [contact]

	
E-mail: [name]
 
[name] HIV Division. Internal Medicine. Hospital del Mar [contact] E-mail: [contact]
 
[name] HIV Division. Internal Medicine. Hospital del Mar. [contact] E-mail: [contact]

SUMMARY

Qualification	Randomized Study to Assess the Impact of Mediterranean Diet Optimization on Metabolic Profile, Immune Activation, and Cardiovascular Risk in People with HIV on ART
Goals	
 - Assess changes in metabolic profile and lipid in the week 24 - immunoactivation profile at week 24 - To assess changes in arterial stiffness levels measured by pulse wave velocity at week 24 - Proportion of participants with >20% decrease in TMAO in week 24 compared to baseline. - Proportion of participants with an increase of >2 points in the MEDAS scale of adherence to the Mediterranean diet at week 24 - Proportion of participants improving on the EQ-5D quality of life questionnaire at week 24 - Assess persistence of all changes from Objective 1 to 6 at Week 48 - To evaluate the presence and composition of coronary atherosclerotic plaque by means of coronary CT angiography before and after the intervention.
Design	Rehearsal clinical randomized open

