Inclusion-exclusion criteria	
Criteria of inclusion:
 
 - Participant \geq 18 years. - Infection by HIV confirmed by serology. - Treatment antiretroviral asset (TAR). - Burden viral undetectable during to the less 12 months (HE allows a blip below 200 copies). - LDL >140 mg/ dL . - Mediterranean Diet Adherence Screener (MEDAS) less than 9 points (adherence low) for ease the detection of changes after the intervention. 
Criteria of exclusion:
 
 - Participants in treatment lipid-lowering. - Treatment with anti-inflammatory chronic. - Hepatitis B, C or Others conditions inflammatory chronicles active. - Hypercholesterolemia familiar No treated. - Hypothyroidism No controlled. - Impossibility of give he consent.
Treatments or interventions	Advice dietary, analysis blood, measurement of the pulse arterial
Variables	
Cholesterol total, cLDL, cHDL, triglycerides
 
Number, size and composition of particles of lipoproteins
 
Anthropometric profile
 
CD 3, CD45, CD4, CD8, CCR7, CXCR3, CCR6, CD103, FOXP3, CD25, CD45RA and CD45RO
 
IL-6, TNF-alpha, IFN-gamma, sCD163, sCD14, MADCAM-1, sCD14 and LPS.
 
Rigidity arterial extent by the speed of pulse
 
Trimethylamine -N-Oxide
 
Scale MEDAS of adherence to the diet Mediterranean

	Atheroma plaque (number of plaques) Plaque composition (% fibrosis, % calcium, % fat) Coronary calcium index
--	--

	Questionnaire of quality of life EQ- 5D
Population and No. subjects	100 patients of the unit of HIV
Participating centers	Hospital of the Sea. Barcelona
Study Description	Study comparative of the intervention dietetics conventional with a personalized dietary intervention
Overall duration from the study	January 2025- December 2026
Duration of the study for the patient	48 weeks

Board 1. Calendar of the study / procedures for a subject

	Screening (max 28 days before baseline visit)	visit (randomization)	W4 (+/- 7d)	W12 (+/-7d)	W24 (+/-7d)	W48 (+14-7d)
Type of visit	In person	In person			In person	In person
Intervention group			Virtual	Virtual		
Cluster control			No visit	No visit		
Informed consent	x					
Criteria of inclusion and exclusion	x					
Demographic data	x					
History medical	x					
Related story with HIV	x					
Exam physical		x			x	x
Anthropometric data		x			x	x
Questionnaires (MEDAS, FFQ, SMAQ, EQ- 5D and IPAQ)	x (only MEDAS)	x			x	x
Concomitant medication	x	x		x	x	x

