5.3. Definition of the variables of study

Main Variables

- Total cholesterol, cLDL , cHDL , triglycerides in mg/ dL . It will be measured at baseline, week 24 and 48.

Secondary Variables

- Number, size and composition of lipoprotein particles by proton magnetic resonance spectroscopy at baseline, week 24 and 48.
- Anthropometric profile (weight, body mass index, abdominal circumference) at baseline, week 24 and 48.
- CD 3,CD 45,CD4,CD8,CCR7,CXCR3,CCR6,CD103,FOXP3,CD25,CD45RA and CD45RO. Quantification in blood in visits basal, 24 weeks and 48 weeks of cells with markers.
- IL-6, TNF-alpha, IFN-gamma, sCD163, sCD14, MADCAM-1, sCD14 and LPS. Quantification in serum in visit basal, 24 weeks and 48 weeks of
- Rigidity arterial extent by the speed of vole of pulse in the visit basal, week 24 and 48.
- Levels of Trimethylamine -N-Oxide serum (TMAO) in the in the visit basal, week 24 and 48.

- Scale MEDAS of adherence to the diet Mediterranean measures in the Baseline visit, week 24 and 48
- Questionnaire of quality of life EQ-5D in the visit basal, week 24 and 48.
- Presence of atheromatous plaque at the coronary level at the baseline visit and at week 48
- Presence of calcium, fibrous and fatty fraction in the coronary plaque at the baseline visit and at week 48
-

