6. PROCEDURES OF THE STUDY

- Pre-screening visit (Recruitment): carried out by the regular doctor in the outpatient clinics of the HIV unit at Hospital del Mar. Potential candidates who meet the inclusion criteria will be identified. They will be given an appointment for: Initial visit: informed consent will be signed, blood tests will be performed with blood samples (to achieve objectives 1 to 6). A comprehensive history of clinical history, HIV infection, and drug history will be taken. Randomization will be carried out following randomization tables according to age, gender, and ART. They will be referred to an intervention consultation.
- Visit 1 (baseline) : anthropometric measurements will be taken, scales predetermined in the study (annexes) will be passed and the measurement of the pulse wave velocity (according to methods described later). A dietary approach will then be carried out with a different visit schedule:

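### Section 5.1's lipid thresholds conflict with the inclusion lists, and Section 6 randomises one visit before four baselines that Board 1 places at the randomisation visit

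*Protocol*

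**What the plan says.** **Lipid entry rule.** Section 5.1 describes the participants as people on antiretroviral treatment "with dyslipidemia (Cholesterol total >200mg/dl either LDL cholesterol >160mg/dl" and not on lipid-lowering drugs. The inclusion list in Section 5.2, repeated in the Summary, asks for LDL above 140 mg/dL and has no total cholesterol limb. In Section 5.2's withdrawal criteria, a screening failure is a consenting patient who "does not meet the inclusion and/or exclusion criteria".

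**Order of randomisation and baseline.** The Summary describes an open design ("Rehearsal clinical randomized open"). Three parts of the protocol then place the early steps differently.

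- Board 1 has a screening visit up to 28 days before baseline, with MEDAS as its only questionnaire. The next column is headed "visit (randomization") and carries bloods, all questionnaires, anthropometry and pulse wave velocity (PWV). It gives no order within that visit.
- Section 6 has an initial visit at which consent is taken, "blood tests will be performed with blood samples (to achieve objectives 1 to 6") and the participant is randomised and referred on. Visit 1 (baseline) then takes anthropometry, the annexed scales and PWV, and the dietary approach follows. The annexes name MEDAS, EQ-5D-5L and SMAQ.
- Section 7 puts consent, the first sample, the questionnaires and randomisation at the selection visit, and mentions anthropometry and PWV only in the next stage.

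Section 5.3 ties the relevant variables to the baseline visit. Its entry for MEDAS reads "Scale MEDAS of adherence to the diet Mediterranean measures in the Baseline visit, week 24 and 48". The one for PWV is worded along the same lines: "Rigidity arterial extent by the speed of vole of pulse in the visit basal, week 24 and 48". EQ-5D is handled likewise, with the entry "Questionnaire of quality of life EQ-5D in the visit basal, week 24 and 48".

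**The concern.** The first conflict means that the population described under the design is not the one the inclusion list admits. Lipids are the trial's main variables, so two different numeric lipid rules leave a reader unable to say from Section 5.1 who is being studied.

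The second is a question of bias. Objectives 1d, 3, 5 and 6 are all judged against a baseline value. In an open trial, a baseline taken after randomisation is fairly read as taken with allocation known to the participant and possibly to the assessor. Any influence of that knowledge on the baseline passes directly into the change score. Questionnaires are the most open to this, anthropometry and instrument-measured PWV less so. A baseline recorded too late cannot be taken again.

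**Working it through.** No simulation is needed. The check is threshold logic, a comparison of sections, and a count.

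**1. The two lipid rules (mg/dL)**

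- Rule A (Section 5.1): total > 200 or LDL > 160.
- Rule B (Section 5.2 and Summary): LDL > 140.
- A but not B: LDL ≤ 140 and total > 200. Example: LDL 125, total 205.
- B but not A: 140 < LDL ≤ 160 and total ≤ 200. Example: LDL 145, total 195.

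Both groups are possible, so neither rule is a looser or stricter form of the other. The protocol gives no lipid distribution from which to size either group.

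**2. Where each step falls**

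| Step | Board 1 | Section 6 | Section 7 |
|---|---|---|---|
| Consent | Screening | Initial visit | Selection visit |
| Randomisation | Baseline visit | Initial visit | Selection visit |
| Baseline bloods | Baseline visit | Initial visit, listed before randomisation | Selection visit |
| MEDAS | Screening and baseline visit | Visit 1 (baseline) | Selection visit, listed before randomisation |
| EQ-5D | Baseline visit | Visit 1 (baseline) | Selection visit, listed before randomisation |
| Anthropometry, PWV | Baseline visit | Visit 1 (baseline) | Next stage |

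The Section 7 entries for MEDAS and EQ-5D assume that its unnamed questionnaires include both. Section 6 is also not consistent with itself on bloods: its group descriptions say that weeks 24 and 48 repeat the baseline visit, blood draws included, yet the bloods were assigned to the initial visit.

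**3. Objectives affected if Section 6 is followed**

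- Items in objectives 1 to 6: 1a, 1b, 1c, 1d, 2a, 2b, 3, 4, 5, 6 = 10.
- Resting on blood: 1a, 1b, 1c, 2a, 2b, 4 = 6. The sample is listed before randomisation.
- Measured at Visit 1, after randomisation: 1d (anthropometry), 3 (PWV), 5 (MEDAS), 6 (EQ-5D) = 10 − 6 = 4, of which 2 are questionnaires.
- Objective 7 carries objectives 1 to 6 to week 48, so the same baselines are used again.

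**4. How a shifted baseline acts on objective 5**

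A responder gains more than 2 MEDAS points. A participant who gains exactly 2 is a non-responder. If the baseline is recorded 1 point lower, the gain becomes 2 + 1 = 3 and the same participant is a responder with no difference in diet. This shows the mechanism only; the protocol gives no basis for the size or direction of any shift.

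**The case against.** On the lipid rule, both formal inclusion lists agree and screening failure refers to them. The outlier is a parenthesis in a one-sentence design description, and patients who meet only that description would not be enrolled. The group meeting only the inclusion list also looks narrow: total ≤ 200 with LDL > 140 leaves less than 200 − 140 = 60 mg/dL for all other cholesterol. This stands as a limit on the harm. It does not remove the contradiction, since Section 5.1 still states thresholds that do not describe the enrolled population.

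On visit order, the case is that post-allocation questionnaires rest on Section 6 alone. Section 7 names the questionnaires before randomisation, Board 1 is silent on order within the visit, and no section says who knows the allocation at Visit 1. A MEDAS score is needed for eligibility, so an earlier value would exist. PWV has automatic quality control and averages two readings. All measurements precede dietary advice, and the main variables are spared.

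Much of this is right and confines the problem to secondary outcomes. It does not dispose of it. Section 6 is the procedures section, which staff can be expected to follow. Section 5.3 makes the baseline visit, not screening, the source of the MEDAS baseline, and EQ-5D has no screening value in Board 1. Knowledge of allocation is an inference, but a reasonable one in a trial declared open. Section 7's different placement is one more inconsistency. It suggests, without proving, that the anthropometry and PWV baselines also follow allocation.

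**Conclusion.** Both points hold. The protocol states two lipid entry rules, neither containing the other. The list in Section 5.2 and the Summary appears to be the operative one, but the document does not say which thresholds are intended.

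The protocol also gives incompatible placements of randomisation and baseline. Followed as written, Section 6 puts the baselines of 4 of 10 items after allocation, 2 of them questionnaire outcomes (objectives 5 and 6), where the risk is greatest. This assumes that allocation is known once made, as the open design implies. The main lipid variables are affected only in that sections differ on which visit supplies the baseline sample. No size is claimed for any bias or for the discordant lipid groups. Both points should be fixed, and the textual contradictions themselves are certain.

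**What to change.** 1. Reconcile the lipid entry rule and print one rule, in identical words, in the Summary, Section 5.1 and Section 5.2. Which thresholds apply is for the investigators to decide.
2. Align Sections 6 and 7 with Board 1. Randomise at the baseline visit, only after eligibility is confirmed and the baseline bloods, questionnaires, anthropometry and PWV are complete. Keep Section 6's rule that dietary advice follows the measurements. Write this order beneath Board 1, and say there where the baseline coronary CT falls, since Board 1 ticks it at the same visit.
3. Name the one visit that supplies the baseline blood sample, in the same words in Board 1, Section 6 and Section 7.

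The cost is protocol wording. No visit, procedure or system is added, because the randomisation step moves to a visit Board 1 already schedules. The sponsor should check whether the staff who perform randomisation change as a result, since Section 7 describes the selection visit and the later measurements as separate stages.

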Objective 1. Evaluate changes in the metabolic and lipid profile:

- Objective 1a. To evaluate changes in the lipid profile (total cholesterol, LDL-C, HDL-C, triglycerides) at week 24 compared to baseline.
- Objective 1b To evaluate the number, size and composition of lipoprotein particles by proton magnetic resonance spectroscopy at week 24 compared to baseline.
- Objective 1c. Percentage of people with increased high-density lipoprotein (HDL) levels >5%.
- Objective 1d. To assess changes in the anthropometric profile (weight, body mass index, abdominal circumference) at week 24 compared to baseline.

Aim 2. Assess changes in he profile inflammatory and of immunoactivation :

- Aim 2a. Assess the changes in the activation immune of the T cell compartment at week 24 compared to baseline.
- Objective 2b. Percentage of patients with reduced inflammatory and bacterial translocation markers at week 24 compared to baseline.

Objective 3. To evaluate changes in arterial stiffness levels measured by pulse wave velocity at week 24 compared to baseline.

Aim 4. Proportion of Participants with decline of >20% of TMAO in the week 24 compared to baseline.

Aim 5. Proportion of Participants with increase of >2 points in the scale MEDAS adherence to the Mediterranean diet at week 24 compared to baseline

Objective 6. Proportion of participants who improve in the quality of life questionnaire. EQ-5D life at week 24.

Objective 7. Evaluate the persistence of all changes included in objectives 1 to 6 at week 48 (24 weeks after the end of the intervention)

Objective 8. To assess the burden of subclinical atherosclerotic coronary disease and changes 1 year after intervention.

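### Section 5.2 makes events that leave outcomes measurable into reasons for leaving the study, so week-24 and especially week-48 data can be lost for good

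*Protocol*

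**What the plan says.** Section 5.2, under the withdrawal criteria, opens its list with "The reasons of abandonment of the study will be the following". Beside screening failure, withdrawal of consent and loss to follow-up, the list contains three events that can occur after randomisation in someone who is still available for measurement:

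- on drug use, "Consumption of anti-inflammatory either lipid-lowering drugs during further of 7 days"
- on newly found disease, "Diagnosis of hypothyroidism either diabetes mellitus"
- on tolerance of the assigned diet, "Any event adverse that prevent continue any diet indicated"

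Just before the list, the investigator is given a discretionary power: "He IP can give of low to a subject of the study by reasons of safety or efficacy". Efficacy is not defined in this context, and the Summary describes the trial as open.

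The entry exclusions in the same section are narrower. They name "Treatment with anti-inflammatory chronic" and "Hypothyroidism No controlled", as well as lipid-lowering treatment. Diabetes is not named.

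On timing, Objective 7 in section 4 is to "Evaluate the persistence of all changes included in objectives 1 to 6 at week 48 (24 weeks after the end of the intervention"). Section 5.3 measures the main lipid variables at baseline, week 24 and week 48, and coronary plaque at baseline and week 48 only. Section 7, item 4, says the 48-week visit takes place for every participant, but does not say whether that includes people who met a withdrawal criterion.

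**The concern.** Stopping an assigned diet and ceasing to be measured are different things, and section 5.2 treats them as one. Starting a lipid-lowering drug, taking a course of anti-inflammatories or being diagnosed with diabetes leaves LDL, inflammatory markers and plaque fully measurable. These events are also plausibly related to those same outcomes.

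Followed as written, the week-48 analyses (persistence under Objective 7, coronary change under Objective 8) would rest on participants who avoided such events. That is selection after randomisation. Who is measured after an event is fixed by the protocol, and a statistical analysis plan can only handle values that were collected.

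**Working it through.** **1. Comparing the provisions**

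- *Is there anything left to stop?* By Objective 7 the intervention ends at week 24. The post-intervention share of follow-up is 24/48 weeks = 50%. In that half, leaving the study stops no study intervention and only removes the week-48 measurement.
- *Do the exit rules mirror the entry rules?* Only the lipid-lowering rule does so fully. Entry excludes chronic anti-inflammatory treatment, but an 8-day course is enough for exit: 8/(48 × 7) = 8/336 = 2.4% of follow-up. Diabetes is a ground for exit but not an exclusion. Controlled hypothyroidism is accepted at entry, while any new diagnosis is a ground for exit.
- *Which outcomes are exposed?* An exit before week 24 loses both later visits. An exit between the visits loses week 48 only. At an assumed 10% per 24-week period, 100 × 0.9 = 90 remain at week 24 and 90 × 0.9 = 81 at week 48, so 10 and 19 are lost. For plaque, any exit after the baseline scan loses the change measurement altogether.
- *Is detection even?* Board 1 schedules concomitant medication and adverse effects at week 12, but the control arm has no visit at weeks 4 or 12. Before week 24, only the intervention arm has study contacts at which a trigger can be noticed.

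**2. Precision (assumed withdrawal rates; arm sizes 67 and 33 from section 6)**

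With kI and kC leaving, the ratio of standard errors is √[1/(67 − kI) + 1/(33 − kC)] / √[1/67 + 1/33].

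| Assumed rate | Leave (67 / 33) | Remain | Ratio |
|---|---|---|---|
| 5% | 3 / 2 | 64 + 31 | 1.029 |
| 10% | 7 / 3 | 60 + 30 | 1.051 |
| 20% | 13 / 7 | 54 + 26 | 1.122 |

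**3. Selection**

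Assume those who leave would have LDL d = 20 to 40 mg/dL above completers in their own arm. The completers' mean in an arm is then the full-arm mean minus (proportion leaving) × d. The completers' difference, intervention minus control, therefore shifts by (kC/33 − kI/67) × d.

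| Leave (intervention, control) | kC/33 − kI/67 | Shift, mg/dL |
|---|---|---|
| 3/67, 5/33 | +10.7 points | +2.1 to +4.3 |
| 10/67, 2/33 | −8.9 points | −1.8 to −3.5 |
| 7/67, 3/33 | −1.4 points | −0.3 to −0.5 |

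**4. The price of keeping these participants**

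Values taken on a lipid-lowering drug are affected by it. The shift is (difference in start rates between arms) × (drug effect on LDL). With an assumed difference of 0, 5 or 10 points and an assumed effect of 20 to 60 mg/dL, it is 0, 1 to 3 or 2 to 6 mg/dL, with the sign set by the arm that starts more often.

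**The case against.** The strongest objection is that the loss of data is inferred. The protocol never says outright that visits cease once a criterion is met, and section 7 promises the 48-week visit to all. The text also reads as a rough translation, which cautions against leaning on single words. This stands in part: the passages are ambiguous together. But leaving the study ordinarily means that its visits end, and section 7 does not mention withdrawn participants. The ambiguity itself needs resolving.

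Second, a new diagnosis of hypothyroidism can be read as disease not yet controlled, which would match the entry exclusion. That is fair. The contrast is firm for diabetes and for short anti-inflammatory courses, and weaker for hypothyroidism.

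Third, stressing week 48 could understate the effect on week 24, where the main lipid change is assessed. This also stands: adverse events that prevent the diet will mostly occur before week 24 and then cost both visits. Week 48 is the more exposed because losses accumulate and because week-24 lipid results can be known by then. That those results prompt drug starts is an inference.

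Fourth, the selection and retention shifts concern different quantities. Leavers' excess LDL is plausible mainly as a drug-free value, whereas retained follow-up would often record on-drug values. The retention shift (up to 6 mg/dL) can exceed the selection shift (up to 4.3 mg/dL). Retention therefore does not simply undo the selection shift. What it does is keep the randomised groups measured and the choice of target quantity open.

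**Conclusion.** The concern holds. Section 5.2 turns events that leave outcomes measurable into reasons for leaving the study, adds an undefined efficacy ground in an open trial, and makes no provision for assessment afterwards. Week-48 outcomes are the most exposed and week 24 is affected to a lesser degree.

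No figure in the protocol is in dispute, and it gives no withdrawal rate, so every size here is illustrative. The precision loss is modest: 3% to 5% in standard error at 5% to 10% withdrawal, and 12% at 20%. The possible LDL shift is a few mg/dL, near zero when the arms lose similar proportions, and its direction depends on which arm loses more. Neither the size nor the direction of the actual bias can be read from the protocol. This should be fixed, since missed visits cannot be recovered later.

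**What to change.** In section 5.2, state that for randomised participants only withdrawal of consent and true loss to follow-up end data collection. Anyone meeting another listed criterion is still invited to the planned week-24 and week-48 assessments, with the event, any drug and its start date recorded. Exempt any procedure judged unsafe for that person or not covered by their consent; CCTA is the obvious case, since it needs intravenous contrast and a specific updated consent (section 3.1; section 6, Task 7). Delete efficacy as a ground for ending follow-up, or define it. In section 7, item 4, say whether the 48-week visit includes those who met a withdrawal criterion. Screen failures are unaffected, and no decision about diet or drug treatment changes.

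The cost is protocol wording and a consent sentence on assessments after a criterion is met. Week-24 and week-48 visits are already planned in both arms, and Board 1 already records medication and adverse effects at both. The downside is that some retained values will be drug-affected and may dilute the estimated diet effect; how to analyse them belongs in the statistical analysis plan.
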